## **7.4.2** Pharmacokinetic Analysis *Not applicable*.

### 7.4.3 Safety Analysis

We will complete quarterly data reviews to examine safety events in the intervention and comparison groups. [name] will advise us if any changes to the existing study protocol are needed to ensure patient safety.

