### 5.2.7 Comparison Group

Participants randomized into the comparison group will receive one 15 to 30-minute diabetes education session. Interventionists (coaches) will read the content of 3 diabetes educational handouts about (1) general descriptions of type 2 diabetes, (2) healthy eating, and (3) physical activity. Handouts are produced in alignment with American Diabetes Association guidelines by a community group (https://learningaboutdiabetes.org/) and have been used in previous diabetes behavioral trials with participants in low-income situations. Participants will receive a standard pillbox at this visit. Participants will receive a resource sheet with referral information to establish health care, mental health support, or to access local resources for housing, food, and other basic needs.

Comparison group participants will be contacted by the study staff (non-interventionists) once-monthly starting 4 weeks after their education session through the final assessment visit. Booster calls will update participant contact information and remind them of the timeline for follow-up assessments.

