### **5.2.8** Follow-up Assessments

The follow-up assessments will be completed by a blinded research staff member. The staff person will assess:

- Vital Signs: BP
- Height and Weight
- Hemoglobin A1c
- Medication review
- Patient-reported measures, see Table 1 for timeline and specific measures

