#### 5.3 Unscheduled Visits

Contact between the study team and participant during the 24-week study period will be encouraged. This will include reminders of study-related assessments and coaching visits.

The interventionist will work with intervention participants to set treatment goals related to improved diabetes care. These may include between-visit text messages, calls, e-mails, or private messages on secure social media platforms per the participant's preference. These will be done with input and agreement by the participant. The interventionist will also respond to participant-initiated between visit communications.

Study staff will respond to participant-initiated communications from comparison group participants. They will refer participants to locally available resources on the handout for any expressed needs.

Should communications become too frequent or surpass agreed upon boundaries with any participants, staff will be guided to set boundaries and limit contact by Drs. [name] and/or [name].

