# **6.3** Pharmacokinetic Evaluation Not applicable

# 6.4 Safety Evaluation

Subject safety will be monitored by adverse events and rates of early termination of the study. We will also follow safety protocols in case we identify dangerous blood pressure, or heart rate values at baseline or follow-up assessment visits. See Section 8 for details.

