#### 8 SAFETY MANAGEMENT

#### 8.1 Clinical Adverse Events

Clinical adverse events (AEs) and serious adverse events (SAEs) will be closely monitored throughout the study in accordance with HHRI IRB definitions and policies.

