# 8.2 Adverse Event Reporting

Unanticipated problems related to the research involving risks to subjects or others that occur during the course of this study and SAEs will be reported to the IRB in accordance with IRB Attachment EEE: Prompt Reporting Guidelines. AEs that are not serious but that are notable and could involve risks to subjects will be summarized and submitted to the IRB at the time of continuing review. Adverse event reports will be reviewed annually with the HHRI IRB to ensure participant safety.

[name] will be responsible for completing Adverse Events Forms should an event occur. She will report Serious Adverse Events to the HHRI IRB within 24 hours of having received notice of the event.

Drs. [name], [name], and [name] will collaboratively gather any information needed to investigate any reported safety events and determine subsequent action. Any subsequent action will be documented and reported to the HHRI IRB and the Program Officer at NIH.

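### Safety events are reviewed by arm, but no listed visit item asks about adverse events and contact differs between arms, so the review is open to detection bias

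*Combined protocol and SAP*

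**What the plan says.** **The review.** Section 7.4.3: "We will complete quarterly data reviews to examine safety events in the intervention and comparison groups". Its stated use is advice on whether the protocol should change for safety reasons. No test, rate or rule for comparing the arms is given. Section 6.4 names the measures: "Subject safety will be monitored by adverse events and rates of early termination of the study".

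**How events are captured.** Section 8.1 says that adverse events and serious adverse events "will be closely monitored throughout the study in accordance with HHRI IRB definitions and policies". Section 8.2 names a person who "will be responsible for completing Adverse Events Forms should an event occur", and the 24-hour clock for serious events starts when notice is received. Neither section gives a question, a recall window or a source of information.

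**What the follow-up visits contain.** Section 5.2.8: "The follow-up assessments will be completed by a blinded research staff member". The list that follows has blood pressure, height and weight, A1c, a medication review, and "Patient-reported measures, see Table 1 for timeline and specific measures". Table 1 has no adverse-event row. It does schedule self-reported health care use at the first baseline visit and at both follow-ups, in both arms.

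**Contacts.** Table 2 gives the coaching arm 10 sessions over 12 weeks and monthly boosters from week 12 to week 24. Section 5.3 adds agreed between-visit messages, and "The interventionist will also respond to participant-initiated between visit communications". The comparison arm has one 15- to 30-minute education session and monthly calls by non-coaching staff, described in section 5.2.7: "Booster calls will update participant contact information and remind them of the timeline for follow-up assessments".

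**The concern.** A by-arm tally of safety events is informative only if an event has a similar chance of being noticed in each arm. As written, events become known passively, and the routes differ by arm. Coaches discuss medication, co-morbid conditions and barriers, and treatment sessions are recorded and reviewed in supervision (section 9.2). The comparison calls have an administrative purpose. A comparison participant who contacts staff with a need is referred to resources on a handout (section 5.3), and no event enquiry or recording is described there.

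At stake is how the quarterly review is read. A difference between arms could reflect who was asked rather than what happened, and events in the less-observed arm could go unseen. The adviser's view on protocol changes rests on this review. The pilot is also meant to refine procedures for a later full trial, so a passive method may be carried forward.

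**Working it through.** The plan states no figure for safety events, detection or safety power, so there is nothing to reproduce. Two checks were made: a count of contacts, and an illustration of what unequal contact could do.

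**1. Planned contacts per participant**

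Inputs: 10 sessions and about 3 boosters (Table 2); two follow-up visits in both arms (Table 1); one education session (section 5.2.7). At four-week spacing the comparison calls number 5 if they run over weeks 6–24 (section 4.3.1) and 7 if they run over weeks 3–30 (Table 2). Section 5.2.7 gives a third window, from 4 weeks after the education session to the final visit.

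- Coaching, full attendance: 10 + 3 + 2 = 15
- Comparison: 1 + 5 + 2 = 8, or 1 + 7 + 2 = 10
- Ratio: 15/10 = 1.5 to 15/8 = 1.9
- Coaching at 50% session attendance (section 7.1): 5 + 3 + 2 = 10, so the ratio is 10/10 = 1.0 to 10/8 = 1.25
- Leaving out the two shared visits: 13/8 = 1.6 to 13/6 = 2.2 at full attendance; 8/8 = 1.0 to 8/6 = 1.3 at 50%

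Between-visit messages are extra and have no stated limit.

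**2. Apparent ratio when true risk is equal**

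Assumptions, none from the documents: onset is uniform over weeks 2.5 to 27; each later contact reveals an event with probability q; each follow-up visit (placed at weeks 14 and 27) reveals it with probability r. For onset at time t, detection = 1 − (1 − q)^n(t) × (1 − r)^m(t), where n(t) counts the arm's own later contacts and m(t) the remaining follow-up visits. This is averaged over t. Sessions are evenly spaced from week 2.5, with the first treated as too early to reveal anything; boosters fall at weeks 16, 20 and 24. Comparison calls fall every four weeks from week 6, either to week 22 (five calls) or to week 30 (seven calls, the same number as under Table 2).

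Follow-up visits revealing nothing (r = 0), full attendance:

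| q coaching | q comparison | Detected, coaching | Detected, comparison (window to week 24) | Ratio | Detected, comparison (window to week 30) | Ratio |
|---|---|---|---|---|---|---|
| 0.1 | 0.1 | 0.32 | 0.21 | 1.56 | 0.35 | 0.91 |
| 0.2 | 0.2 | 0.50 | 0.36 | 1.37 | 0.59 | 0.85 |
| 0.3 | 0.3 | 0.61 | 0.48 | 1.26 | 0.74 | 0.82 |
| 0.3 | 0.1 | 0.61 | 0.21 | 2.95 | 0.35 | 1.72 |
| 0.2 | 0.05 | 0.50 | 0.11 | 4.54 | 0.19 | 2.56 |

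Ratios are from unrounded values. With equal yield per contact, the direction depends on the call window, because calls after week 24 pick up late events once boosters have stopped. If the administrative calls yield less, coaching appears worse under either window.

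**3. Effect of asking at the shared visits**

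| Yield of each follow-up visit | Ratio, window to week 24 | Ratio, window to week 30 |
|---|---|---|
| r = 0 | 1.26–4.54 | 0.82–2.56 |
| r = 0.5 | 1.05–1.20 | 0.92–1.13 |
| r = 0.9 | 1.00–1.02 | 0.99–1.01 |

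**4. Scale in this trial**

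With 54 participants allocated 1:1 there are 27 per arm. If true risk were 30% in both arms, and detection 75% against 50%, recorded events would be 27 × 0.30 × 0.75 = 6.1 and 27 × 0.30 × 0.50 = 4.1. A two-sided 5% test would flag that about 10% of the time. No such test is planned; the figure shows that an artefact of this size would look like chance variation, not like a fault in ascertainment.

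**The case against.** The case on the other side is substantial.

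- **Some capture is the same in both arms.** Health care use is asked at both blinded follow-ups. The MHI-5 at the same visits bears on worsening mental health, a risk named in section 9.4.2. Abnormal blood pressure or heart rate at assessment visits triggers a safety protocol (section 6.4). Claims on hospital and emergency use are sought for all participants (section 6.1). Early termination, the other safety measure, depends little on contact frequency.
- **No formal comparison is stated.** The review is oversight in a small study expected to be minimal risk.
- **Comparison participants may also initiate contact**, and section 5.3 encourages contact during the study.
- **Some material is unseen.** The full assessment questionnaire is attached separately, and section 8.1 defers to IRB policies. An event question in either cannot be ruled out.

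This stands as far as it goes. A reader might infer that no visit yields any safety information; the documents do not support that, because hospital and emergency use is covered in both arms. What remains is that no section links the health-care-use answers to the safety review: section 7.4.1 treats them as an outcome to model. Claims arrive only at study end, too late for quarterly reviews. Neither source reaches events for which no care was sought. A review by arm that can prompt protocol changes needs comparable ascertainment even without a test.

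**Conclusion.** The point holds in limited form. On the plan as written, the by-arm safety review is open to detection bias, mainly for events that do not lead to hospital or emergency care. This rests on three features of the text: no listed item asks about adverse events, capture is passive, and planned contacts differ in number and content.

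A reader might go further and infer that the coaching arm will show a 1.5- to 1.9-fold excess of events. The documents do not support that. The figure is a ratio of contacts, and it becomes an event ratio only if all sessions are attended and detection is proportional to contacts. At the accepted 50% attendance the contact ratio is 1.0 to 1.25 before messages, and with equal yield per contact and calls to week 30 the direction reverses (0.82–0.91). The larger ratios depend on assumed differences in yield per contact. The size and direction therefore remain open, and the inconsistent call window is part of the reason.

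**What to change.** - **Ask.** Add one scripted adverse-event question, with recall since the last assessment, to follow-up visits 1 and 2 in Table 1 and section 5.2.8, asked by the blinded assessor in both arms. If the separate questionnaire already has one, cite it there.
- **Link.** State in section 7.4.3 that the existing health-care-use answers feed the safety review. No new hospital or emergency question is needed.
- **Record the source** of each event: visit, coaching, call or records.
- **Summarize like with like.** Base any between-arm summary on events from the shared visits plus health-care-use data and, at study end, claims. List separately the events learned only through coaching or other contact. All events are still reported and acted on as they arise.
- **Reconcile** the comparison-call window across Table 2, section 4.3.1 and section 5.2.7.

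The cost is about a minute per existing visit and one row in Table 1, with no added visits. Two limits remain. Visit-based data will be missing for participants who miss follow-up, so claims and the separate listing are still needed. Visits at weeks 12–16 and 24–30 will not supply each quarterly review evenly, so the running list of reported events must continue alongside them.

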#### 7.5 Sample Size and Power

This sample size is appropriate for the goal of feasibility and acceptability of the intervention. This is in line with ongoing studies by [name] (HSR#17-4351) as well as the current literature.

#### 8 SAFETY MANAGEMENT

#### 8.1 Clinical Adverse Events

Clinical adverse events (AEs) and serious adverse events (SAEs) will be closely monitored throughout the study in accordance with HHRI IRB definitions and policies.

# 8.2 Adverse Event Reporting

Unanticipated problems related to the research involving risks to subjects or others that occur during the course of this study and SAEs will be reported to the IRB in accordance with IRB Attachment EEE: Prompt Reporting Guidelines. AEs that are not serious but that are notable and could involve risks to subjects will be summarized and submitted to the IRB at the time of continuing review. Adverse event reports will be reviewed annually with the HHRI IRB to ensure participant safety.

[name] will be responsible for completing Adverse Events Forms should an event occur. She will report Serious Adverse Events to the HHRI IRB within 24 hours of having received notice of the event.

Drs. [name], [name], and [name] will collaboratively gather any information needed to investigate any reported safety events and determine subsequent action. Any subsequent action will be documented and reported to the HHRI IRB and the Program Officer at NIH.

# 8.3 Investigator Reporting of a Serious Adverse Event to Sponsor

Reporting to the National Institutes of Health will be completed as required by their policies or advised by HHRI IRB staff.

# 8.4 Medical Emergencies

If non-urgent psychological distress arises in participants during study related activities, study staff will provide a handout about local mental health resources, including a 24-hour support line and psychiatric emergency room (See *Resource List*). If non-urgent physical health needs arise in participants, study staff will provide written resources about health care available through Health Care for the Homeless and Hennepin Healthcare (See *Resource List*).

If an emergency physical or behavioral health situation arises, study staff will arrange for immediate clinical support from PI ([name]), Health Care for the Homeless clinical staff (who have a walk-in treatment model), the Hennepin County mental health crisis team (COPE Line, available by phone or in-person 24hrs./day, 7 days/week), or emergency medical services as appropriate. This event will be written up and reviewed by the PI ([name]) and primary mentor ([name]) within 48 hours of the event and reported to the IRB if needed.

If measured blood pressure surpasses SBP>180 or DBP>100 if blood sugar measurement takes place within a study visit and falls <60 or >400/error, study staff will page [name] who will provide clinical assessment of symptoms and make referral or arrangement for immediate transfer to appropriate treatment as needed.

As deemed necessary by the primary mentor and/or HHRI IRB, issues related to patient safety will be reviewed with mental health or medical professionals at HCMC not affiliated

with the study who will provide recommendations for withdrawal from the study, referrals for additional care, or other necessary action.

### 9 STUDY ADMINISTRATION

## 9.1 Treatment Assignment Methods

- **9.1.1 Randomization or Other Assignment** Randomization will occur at the 2nd baseline visit, and will be done using a pre-generated randomization schedule in REDCap. Randomization will be stratified into 2 strata based on severity of housing instability: "unstable" (e.g., living in shelter, staying outside) and "more stable" (e.g., history of homelessness that's now resolved, worry about rent payment, subsidized housing).
- **9.1.2 Blinding** Staff who conduct the follow-up assessment visits will be blind to condition.
- **9.1.3 Unblinding** Multiple staff members will be trained in how to complete the outcome assessments. In the event that a staff member is unblinded during the first follow-up assessment visit, a different blinded assessor will complete the 24-week visit.

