### 4.2 Allocation to Groups and Blinding

Participants will be randomized to either the intervention or a control group (1:1). Randomization will be stratified by housing type (unstable (e.g., shelter, staying outside) vs.

more stable (e.g., worry about rent payment, supportive or transitional housing)). Randomization will occur after baseline assessment visit #2 via REDCap. Staff who conduct who conduct the follow-up assessment visits will be blind to condition.

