# 4.3.2 Total Number of Study Sites/Total Number of Subjects Projected

Enrollment for the study will continue until 54 participants have been enrolled.

HHRI will serve as the only site for this study.

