#### 7 STATISTICAL CONSIDERATIONS

# 7.1 Primary Endpoint

The primary endpoint of this study is the satisfaction of participants in this pilot randomized trial (via CSQ-8).

The feasibility and acceptability of study protocols for recruitment, retention, and randomization are also important. We will assess this by measuring our ability to recruit and retain participants, and the assessment and treatment visits we can deliver (i.e., participant's attendance and follow-up with scheduled sessions and treatment activities). In addition to above outcomes, we will carefully track the number and types of between-treatment communications with participants (who initiated communication; form of communication: text, calls, e-mails, etc.).

We will consider the study feasible if we enroll 75% of those screened who meet inclusion criteria, and 75% of enrolled participants complete at least one follow-up. We will consider 50% session attendance as indicative of feasibility. We will consider the intervention acceptable if 70% of participants are satisfied and would recommend it to others.

We will also analyze our primary clinical endpoint of change in A1c between intervention and comparison groups between baseline follow-up visit #1 (approx. 12-16 weeks)

if it changes from baseline to between intervention.

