# 7.4.1 Efficacy Analysis

We will use summary statistics (mean, standard deviation) to examine CSQ-8 scores for all participants. We will use t-tests to examine the differences in CSQ-8 scores between the intervention and comparison groups; we hypothesize no difference. We will also examine the experiences of White vs. Black, Native American, and Hispanic participants. We will also generate summaries of the age, gender, and race/ethnicity of people at the highest and lowest quintiles of CSQ-8 scores.

We will use generalized linear models to compare changes in A1c and medication adherence (ARMS-D and ASK-12) over time in intervention vs. comparison groups. We will control for baseline differences and changes in housing status over time. Adherence will also be examined with pharmacy refill data which we will compare to self-report (ARMS-D and ASK-12). We will use an intention-to-treat approach including all randomized participants; multiple imputation will generate data for those lost to follow-up. Similar modeling approaches will compare psychological wellness, blood pressure, and health care use outcomes.

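### The randomisation stratum (housing stability) is left out of the CSQ-8 t-test and is not clearly named in the outcome models, which loses precision if it predicts the outcome

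*Combined protocol and SAP*

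**What the plan says.** Stratification is stated twice. Section 4.2 has "Randomization will be stratified by housing type", contrasting unstable with more stable housing at 1:1 allocation. Section 9.1.1 has "Randomization will be stratified into 2 strata based on severity of housing instability". On the mechanics, section 9.1.1 adds only that it "will be done using a pre-generated randomization schedule in REDCap"; no block size or other restriction within strata is given.

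Section 7.1 makes CSQ-8 satisfaction the primary endpoint. Section 7.4.1 gives its only between-arm analysis: "We will use t-tests to examine the differences in CSQ-8 scores between the intervention and comparison groups", with the expectation that the arms will not differ. No covariate is mentioned.

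For A1c, ARMS-D and ASK-12, section 7.4.1 and the synopsis plan generalized linear models of change. These control for baseline differences and for how housing status changes during follow-up. Similar models are planned for psychological wellness, blood pressure and health care use, with multiple imputation for participants lost to follow-up. Neither the models nor the imputation step name the stratum.

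**The concern.** Stratifying within balanced blocks removes between-stratum variation from the true variance of the arm difference. A two-sample t-test still counts that variation in its estimated variance, so the interval is wider than it needs to be and the test rejects less often than its nominal level. Even without blocking, a predictive baseline factor left out of the model is precision forgone, which matters with 54 participants.

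For CSQ-8 a wide standard error is not simply cautious. The plan expects no difference, so excess width favours the expected result.

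In the outcome models the difficulty is ambiguity. Baseline differences could mean observed imbalances, and the stratum is the variable least likely to be imbalanced after stratification. It could also mean baseline housing, but then the analyst might use the 30-day housing item in Table 1 instead of the stratum. Change in housing is measured after randomisation and does not carry the baseline level.

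**Working it through.** The plan has no figure to reproduce: it states no alpha, power, effect size or SD.

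**Inputs from the documents.** 54 participants ("Enrollment for the study will continue until 54 participants have been enrolled"), two strata, 1:1 allocation. For a lower-retention scenario, the feasibility threshold "75% of enrolled participants complete at least one follow-up" is used as 75% completers.

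**Assumptions.** Two-sided 0.05; SD 1; normal outcome; one third in the unstable stratum; blocks of 4 or no blocking within strata; share of outcome variance explained by the stratum (R²) 0.05, 0.10 or 0.20; dropout at random; completers only, without imputation.

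**Large-sample formulas, balanced blocks.** With everyone analysed, the ratio of estimated to true standard error is k = 1/√(1 − R²). True type I error is 2 × (1 − Φ(1.96k)). At R² = 0.20, k = 1/√0.80 = 1.118 and type I error is 0.028.

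Random dropout partly undoes the balance. For n participants in a stratum and retention r, the variance of the arm imbalance among completers is n·r·(1 − r) under blocking and n·r without it. A fraction 1 − r = 0.25 of the between-stratum variation therefore returns, and k = 1/√(1 − 0.75R²). At R² = 0.20, k = 1/√0.85 = 1.085 and type I error is 0.034.

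**Simulation, blocks of 4** (60,000 trials per setting; error on type I error about ±0.002). Formula values are in parentheses.

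| R² | SE ratio, all 54 | Type I, all 54 | SE ratio, 75% | Type I, 75% |
|---|---|---|---|---|
| 0.05 | 1.023 (1.026) | 0.044 (0.044) | 1.015 (1.019) | 0.045 (0.046) |
| 0.10 | 1.045 (1.054) | 0.039 (0.039) | 1.033 (1.040) | 0.041 (0.042) |
| 0.20 | 1.107 (1.118) | 0.030 (0.028) | 1.073 (1.085) | 0.035 (0.034) |

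With the stratum in the model, type I error is 0.049 to 0.050 in all six settings. Equal strata give nearly the same results. Runs with fewer trials put the last type I figure between 0.030 and 0.040.

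**Simulation, no blocking.** The t-test's type I error is 0.048 to 0.052 throughout, so it is nominal. The mean standard error with all 54 still falls on adjustment: 0.273 to 0.269, 0.274 to 0.262 and 0.274 to 0.247 at R² of 0.05, 0.10 and 0.20.

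**Power at a 0.7 SD difference, all 54, t-test versus adjusted** (illustrative, since the plan names no effect).
- Blocks of 4: 72% versus 76% at R² 0.10; 73% versus 81% at R² 0.20.
- No blocking: 71% versus 74% at R² 0.10; 70% versus 79% at R² 0.20.
- R² = 0: adjustment loses less than one percentage point under either scheme.

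**The case against.** A reader might infer that housing stability appears in none of the planned analyses, and that every standard error is therefore too wide. The documents do not support that, for four reasons.

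First, the outcome models do mention housing. Their covariate wording can be read as baseline housing plus change in housing, and housing is recorded at baseline and at both follow-ups. The supportable criticism is that the covariate is unclear and partly post-randomisation.

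Second, the inflated standard error depends on restriction within strata. A pre-generated REDCap schedule may be blocked, and stratifying achieves little otherwise, but the plan does not say so.

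Third, no document says that housing stability predicts CSQ-8 or A1c change. Section 2 reports that treatment engagement lessened at the highest instability in a single-arm study of 10 to 15 people. Engagement is a different outcome, and the comparison arm has only one session. A1c and adherence are also analysed as change, so a stable difference in level between strata drops out; only prediction of change would matter.

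Fourth, this is a pilot that calls itself under-powered for efficacy. Its success rules are percentages for enrolment, follow-up, attendance and satisfaction, and none uses these standard errors. No equivalence margin or decision rests on the CSQ-8 test.

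All four points stand, and they limit the size of the concern. They do not bring the stratum into the CSQ-8 test or settle what the model covariate means. The trial still plans between-arm tests and a primary clinical endpoint of A1c change, in preparation for a fully powered study.

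**Conclusion.** The point holds in a limited, conditional form. The CSQ-8 comparison omits the stratification factor, and no planned analysis clearly includes the stratum as randomised.

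Two conditions govern the consequence. If housing stability predicts the outcome, precision is lost under any assignment scheme. If assignment is also blocked within strata, the t-test is conservative. Over the assumed R² range of 0.05 to 0.20, its standard error is then about 2% to 12% too wide with all 54 analysed (type I error about 0.044 to 0.03) and about 1% to 7% too wide with 75% completers (about 0.045 to 0.035). Without blocking there is no distortion of type I error, only lower power.

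These figures are for the t-test. The size of any effect on the A1c and adherence models cannot be given, because their covariates are not specified. The feasibility and acceptability criteria are untouched. This is a cheap improvement to the analysis text and no threat to the pilot's main conclusions.

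**What to change.** In section 7.4.1:

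- Replace the CSQ-8 t-test with a linear model of CSQ-8 on arm and randomisation stratum, reporting the adjusted difference with its 95% CI.
- Name the baseline stratum, as recorded in REDCap at randomisation, as a fixed covariate in every between-arm model. State separately what baseline differences means and how the post-randomisation housing term is used.
- Include the stratum in the imputation model.

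In section 9.1.1, state whether assignment is blocked within strata (the block size can be kept from staff who enrol).

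The cost is a few sentences and one degree of freedom per model. No new data are needed, because the stratum must already be recorded in order to randomise. If housing turns out not to predict the outcome, the loss of power is under one percentage point in the settings above.
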